10.1.9.2 Storage

Please refer to the package insert or the most current version of the Investigator Brochure for details.

10.1.9.3 Dispensing of Study Drug

The Study drug provided in accordance with this Protocol will be kept in a secure place, and will only be supplied to patients participating in this Study. The PI is accountable for all Study drug supplied by Genentech in accordance with this Protocol. In addition, the PI must keep accurate and up-to-date dispensation records. Any Study drug accidentally or deliberately destroyed must be recorded in a timely fashion, including an explanation for the destruction in writing. Any discrepancies between the amounts of Study drug dispensed and returned must also be explained in writing. All such records of drug accountability must be entered on the corresponding Patient CRF's.

10.1.9.4 Destruction of Study Drug

All unused and partially used Study drug must be sealed and returned to the PI or his/her designee, or destroyed on Site in accordance with the established procedures for drug destruction, and with approval by the PI or his/her designee. Details of destruction, including, but not limited to, the number of boxes destroyed, batch number, and the date and method of destruction must be recorded on the Study drug destruction logs.

11. STUDY CALENDAR

The schedule of assessments is detailed in Table 10 below.

Baseline evaluations are to be conducted within 2 weeks prior to start of protocol therapy. Scans must be done \leq 2 weeks prior to the start of therapy. In the event that the patient's condition is deteriorating, laboratory evaluations should be repeated within 48 hours prior to initiation of the next cycle of therapy.

Unless otherwise noted below, all assessments (e.g., labs, imaging, physical exam, vitals, etc.) will follow the CPDM departmental SOP "Guidelines for Timing of Protocol Required Procedures". Any activities that would fall within those pre-determined windows will not be considered deviations/violations of protocol procedures.

11.1 Pharmacokinetics Assessments

On days with PK assessments, patients should not eat breakfast or take cobimetinib or hydroxychloroquine at home. Upon arrival to the clinic after undergoing pre-dose PK draw, they will take medications with a glass of milk and eat breakfast, as instructed by clinic staff.

Columbia University Irving Medical Center
Herbert Irving Comprehensive Cancer Center
AAAS4165_Version Date: 07/07/2021

Table 9. PK Assessments

| Treatment Cycle | Day | PK Sample # Hydroxychloroquine (HCQ) ^a (Whole Blood) | PK Sample # Cobimetinib (Cobi) ^a (Plasma) | Time Relative to Dose |
|-----------------|-----|--|---|-----------------------|
| 1 | 1 | 101 | 201 | Pre-dose ^b |
| 1 | 1 | 102 | 202 | 1hr ± 5 min |
| 1 | 1 | 103 | 203 | 2hr ± 5 min |
| 1 | 1 | 104 | 204 | 4hr ± 5 min |
| 1 | 8 | 105 | 205 | Pre-dose ^b |
| 1 | 8 | 106 | 206 | 1hr ± 5 min |
| 1 | 8 | 107 | 207 | 4hr ± 5 min |
| 1 | 15 | 108 | 208 | Pre-dose |
| 1 | 15 | 109 | 209 | 1hr ± 5 min |
| 1 | 15 | 110 | 210 | 4hr ± 5 min |
| 2 | 1 | 111 | 211 | Pre-dose |
| 2 | 1 | 112 | 212 | 1hr ± 5 min |
| 2 | 1 | 113 | 213 | 4hr ± 5 min |
| | | | | |
| N/A | N/A | 5101+ | 5201+ | Anytime ^c |

^a Hydroxychloroquine (HCQ) will be measured in whole blood and Cobimetinib will be measured in plasma

^b Pre-dose levels should be drawn just prior to administration of Cobimetinib (Cobi) and Hydroxychloroquine (HCQ)

^c Unscheduled doses related to other issues will be sequentially numbered as shown

Columbia University Irving Medical Center
Herbert Irving Comprehensive Cancer Center
AAAS4165_Version Date: 07/07/2021

Table 10. Schedule of Assessments

| Procedure | Screening | Cycle 1 | | | | Cycle 2 | | Cycle 3 | | Cycle 4 and on (every 28 days) | | EOS ² | Follow-up ³ | |
|--|-----------|------------------------|-------------|-------------|--------------|--------------|-------------|--------------|-------------|--------------------------------|-------------|------------------|------------------------|--|
| | | (21 days) ¹ | D1 (±3d) | D8 (±3d) | D15 (±3d) | D22 (±3d) | D1 (±3d) | D15 (±3d) | D1 (±3d) | D15 (±3d) | D1 (±3d) | D15 (±3d) | | |
| Consent | X | | | | | | | | | | | | | |
| Medical history | X | | | | | | | | | | | | | |
| Cytology/pathology/mol. conf. ⁴ | X | | | | | | | | | | | | | |
| Physical exam ⁵ , vital signs | X | X | X | X | X | X | X | X | X | X | X | X | | |
| Height | X | X | X | X | X | X | X | X | X | X | X | X | X | |
| Weight | X | X | X | X | X | X | X | X | X | X | X | X | X | |
| ECOG perf. status | X | X | X | X | X | X | X | X | X | X | X | X | X | |
| ECG ⁶ | X | | | X | | X | | X | | X | | | X | |
| LE Doppler Ultrasound | X | | | | | | | | | | | | | |
| ECHO or MUGA ⁷ | X | | | | | | X | | | | | | X | |
| CBC with differential ⁸ | X | X | X | X | X | X | X | X | X | X | X | X | | |
| Comprehensive metab. panel ⁸ | X | X | X | X | X | X | X | X | X | X | X | X | X | |
| Ophthalmologic exam ⁹ | X | | | | | | | | X | | X | | X | |
| PT/PTT | X | | | X | | | | | | | | | | |
| Fresh tumor biopsy ¹⁰ | X | | | X | | | | | | | | | X | |
| TSH, free T4, cortisol ¹¹ | X | | | | | X | | X | | X | | | X | |
| Viral Serology ¹² | X | | | | | | | | | | | | | |
| C-reactive protein | X | | | | | | | | | | | | | |
| LDH | X | | | | | | | | | | | | | |

Columbia University Irving Medical Center
Herbert Irving Comprehensive Cancer Center
AAAS4165_Version Date: 07/07/2021

| | | | | | | | | | | | | |
|---|---|---|---|---|---|---|---|---|---|---|---|---|
| CPK | X | | | | X | | X | | X | | X | |
| Ca 19-9 and/or CEA | X | | | | X | | X | | X | | X | |
| Pregnancy test ¹³ | X | | | | | | | | | | | |
| Urinalysis | X | | | | | | | | | | | |
| PBMC samples ¹⁴ | X | | | X | | | X | | | | X | |
| Tumor response assessment ¹⁵ | X | | | | | | X | | | | X | |
| Concomitant medications | X | X | X | X | X | X | X | X | X | X | X | |
| Adverse Events | | X | X | X | X | X | X | X | X | X | X | X |
| Atezolizumab administration ¹⁶ | | X | | X | | X | X | X | X | X | X | |
| Dispense cobimetinib | | X | | | | X | | X | | X | | |
| Dispense hydroxychloroquine | | X | | | | X | | X | | X | | |
| Dispense Enoxaparin | | X | | | | X | | X | | X | | |
| Review of dosing diary | | | X | X | X | X | | X | | X | | X |
| Survival follow-up | | | | | | | | | | | | X |
| Blood sampling for PK/PD ¹⁷ | | X | X | X | | X | | | | | | |

1. Protocol-specified screening procedures that are performed as part of standard of care and within 21 days of Day 1 of Cycle 1 may be used for screening purposes. Clinical laboratory studies and baseline CT scan must be performed within the 14-day period before Day 1 of Cycle 1. Screening labs may be used for Cycle 1 Day 1 if performed within 72 hours prior to study visit.
2. The End-of-Study (EOS) visit should be scheduled within the 28-day period after the last dose of study drug and before starting any new anti-neoplastic therapy.
3. A post-study follow-up contact by phone by site staff will be conducted every 3 months during years 1 and 2, then every 6 months thereafter to obtain information on any new anti-cancer therapy received and survival status.
4. Initial diagnosis of adenocarcinoma and KRAS mutation status needs to be confirmed by a CLIA certified pathology.
5. A complete physical examination will be performed at screening. All subsequent physical examinations will be disease-specific on Cycle 1 days 1, 8, 15, 22; Cycle 2 and 3 days 1 and 15; day 1 and 15 on each subsequent cycle, and at the End-of-Study visit.
6. ECG will be performed after the patient has been in a supine position for at least 5 minutes. It will be performed at screening, cycle 1 day 15, day 1 of every subsequent cycle, and at the End-of-Study visit.
7. ECHO or MUGA scan should be performed at screening, day 1 of cycle 2, every 3 months (+ 1 week) thereafter and at the end of study visit.

Columbia University Irving Medical Center
Herbert Irving Comprehensive Cancer Center
AAAS4165_Version Date: 07/07/2021

8. A complete blood count with differential and comprehensive metabolic panel including glucose, calcium, albumin, total protein, sodium, potassium, CO2 (carbon dioxide, bicarbonate), chloride, BUN (blood urea nitrogen), creatinine, ALP (alkaline phosphatase), ALT (alanine amino transferase), AST (aspartate amino transferase) and bilirubin will be performed on Cycle 1 days 1, 8, 15, and 22; Cycle 2 and 3 days 1 and 15; on day 1 and 15 of each subsequent cycle, and at the End-of-Study visit.
9. An Ophthalmologic examination should be performed during the screening period, and on cycle 3 day 1 (+ 7 days), every 12 weeks (+ 7 days) thereafter, and at the End-of-Study visit if not performed within 6 weeks. The baseline exam should include: best corrected distance visual acuity (BCVA), an automated threshold visual field (VF) of the central 10 degrees (with retesting if an abnormality is noted), and spectral domain ocular coherence tomography (SD-OCT). Each subsequent examinations should include BCVA, VF and SD-OCT. In patients of Asian descent, it is recommended that visual field testing be performed in the central 24 degrees instead of the central 10 degrees.
10. Fresh core tumor biopsy will be performed: (1) within 14 days of starting therapy but at least three days prior to starting therapy; (2) Cycle 1 week 3 (day 15-21); and (3) If the patient allows, at progression (within 4 days of discontinuation of therapy).
11. TSH, free T4, and AM cortisol will be assessed at screening, Day 1 of each cycle starting at C2, at end of study, and as clinically appropriate.
12. At screening, patients without a prior positive HIV test result will undergo an HIV test, unless not permitted per local regulations. Patients will also be tested for HBsAg, HBsAb, total HBcAb, and HCV antibody. If a patient has a negative HBsAg test and a positive total HBcAb test at screening, an HBV DNA test should be performed. If a patient has a positive HCV antibody test at screening, an HCV RNA test must also be performed to determine if the patient has an active HCV infection.
13. For women of child-bearing potential, a screening serum pregnancy test must be negative within 7 days of Day 1 of Cycle 1.
14. Peripheral blood mononuclear cells will be collected during screening, cycle 1 day 15, cycle 3 day 1, every eight weeks (+ 7 days), and at End-of-Service visit.
15. CT scan with contrast of the chest, abdomen, pelvis or CT chest and MRI of abdomen/pelvis, PET/CT, or appropriate imaging of disease site to assess tumor status will be performed. Imaging should be performed at the designated time for tumor assessment +/- 7 days. End of study needs not be performed if patient has radiological evidence confirming progression, but needs to be performed if patient coming off study for other reasons, except due to fatality.
Phase 1 –Imaging to be performed every 8 weeks (+ 7 days)
Phase 2 –Pancreas adenocarcinoma –Imaging to be performed every 8 weeks (+ 7 days)
Colorectal adenocarcinoma – Imaging to be performed every 12 weeks (+ 7 days)
Histology agnostic adenocarcinoma – Imaging to be performed every 8 weeks (+ 7 days)
16. The initial dose of atezolizumab will be delivered over 60 (+/- 15) minutes. Subsequent infusions will be delivered over 30 (+/-10) minutes if the previous infusion was tolerated without infusion-associated adverse events, or 60 (+/- 15) minutes if the patient experienced an infusion-associated adverse event with the previous infusion.
17. For pharmacokinetic (PK) analysis, whole blood for hydroxychloroquine and plasma for cobimetinib will be obtained on –
Cycle 1 Day 1 - Pre-morning dose, 1, 2, and 4 hours post-morning dose.
Cycle 1 Day 8 - Pre-morning dose, 1, and 4 hours post-morning dose.
Cycle 1 Day 15- Pre-morning dose, 1, and 4 hours post-morning dose.
Cycle 2 Day 1 - Pre-morning dose, 1, and 4 hours post-morning dose.

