4. STUDY DESIGN

4.1 General Design

4.1.1 Phase 1

The objective of this study is to determine the maximum tolerated dose (MTD) of the combination of cobimetinib, atezolizumab, and hydroxychloroquine. We will evaluate three dose combinations. Patients will be treated with combination therapy at the designated dose levels depicted in Table 1, based on a 28 day cycle (Section 7.3). The MTD is defined as the dose associated with a target probability of dose limiting toxicity of 0.30. The primary endpoint is DLT in the first cycle of treatment.

Columbia University Irving Medical Center
Herbert Irving Comprehensive Cancer Center
AAAS4165_Version Date: 07/07/2021

Given that cobimetinib is approved at a dose of 60 mg orally daily and hydroxychloroquine was well tolerated at 600 mg orally twice daily, we feel that the combination will be well tolerated (Wolpin et al., 2014). Cobimetinib and atezolizumab were tested in advanced colorectal cancer in IMblaze370, a large randomized phase 3 clinical trial (Eng et al., 2019) with proportion of patients experiencing grade 3 and over adverse events similar to those who received the FDA approved Regorafenib. Subjects will receive cobimetinib in cohort 1 and 2 at a lower dose (40mg oral daily) compared to that tested in IMblaze370 (60mg oral daily). Given that, other than ocular and hepatic toxicity, hydroxychloroquine has little to no overlapping adverse events with cobimetinib and atezolizumab, we do not anticipate significant toxicities with this combination at the doses being tested. Ocular toxicities with hydroxychloroquine are observed at high cumulative doses and will be monitored by required scheduled ophthalmological evaluations throughout the study period. We will initiate Phase 1 at dose level 1 using a combined 3+4 and time-to-event continual reassessment method (TITE-CRM). Table 1. Cohort dose levels.

| Patient No. | Dose Level | Hydroxychloroquine (mg) (oral; 1200mg/day; Days 1-28) | Cobimetinib (mg) (oral; 40-60mg/day; Days 1-21) | Atezolizumab (mg) (IV; 840mg every two weeks) |
|------------------|------------|---|---|---|
| 1, 2, 3 | 1 | 600mg twice per day | 40mg | |
| 4, 5, 6 | 2 | 600mg twice per day | 40mg | 840mg |
| 7, 8, 9 10-18 | 3 | 600mg twice per day TITE-CRM | 60mg | 840mg |

Phase I Statistical Considerations

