of 18. The prior distribution of the model parameter is assumed to be normal with a mean of 0 and a variance of 1.34. The dose-toxicity model is calibrated such that the eventual dose yields between 18% and 32% DLT (Cheung & Chappell, 2002; Lee & Ying Kuen, 2009) and good operating characteristics across a wide range of potential scenarios of toxicity profiles. Given that the majority of the toxicities for the cobimetinib and atezolizumab trial occurred in the first cycle of treatment, the proposed toxicity evaluation period is 4 weeks. In the first stage, each cohort will be followed for the entire 4 weeks in the absence of a DLT. Once a DLT is observed, we will impose a minimum of 1 week of observation between patients in the second stage of the design. We do not allow for dose skipping during dose escalation or escalation immediately after a dose limiting toxicity. **Patients who do not complete 80% of dosing due to reasons other than treatment-related toxicity (e.g. non-compliance) will need to be replaced. Moreover, patients who discontinue due to reasons other than treatment-related toxicity (i.e. progression or death) prior to completing 4 weeks of therapy without having experienced a DLT will be considered not evaluable and be replaced.** Partial toxicity information from subjects that are greater than 80% compliant may be included for dose assignments and will continue to be used for future dose assignments unless the patient is not evaluable and/or discontinues prior to the 4 week DLT evaluation. To evaluate the performance of the method, 2000 simulations under these scenarios of toxicity profiles were done. The operating characteristics of our design under these scenarios are displayed in Table 2. Based on these simulation results, the 18-patient design selects the correct MTD with probabilities over 53% under all possible scenarios. These simulations assume that the patients arrive at a rate of 4 patients every 4 weeks (i.e., a patient every week) which is our full toxicity evaluation window, and that a DLT occurs randomly and uniformly

Columbia University Irving Medical Center
Herbert Irving Comprehensive Cancer Center
AAAS4165_Version Date: 07/07/2021

within the observation window. Moreover, based on the various simulation scenarios, we expect

[figure not shown]

Figure 5. Simulated trial using time-to-event continuous reassessment method.

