Each number represents an enrolled patient. Circled numbers depict time at which toxicity was experienced by that patient.

between 6 and 11 of the 18 patients will be assigned the MTD.

To illustrate the method using an example, Figure 5 displays a simulation of a sample design using the method based on scenario 2 (see Table 2), where the true MTD is dose level 2. In this simulated example, the recommended dose level is 2. The first three patients are assigned to dose level 1 in weeks 1, 2, and 3. By week 4 patient 1 has a DLT and we initiate the TITE-CRM with patients 4, 5, 6, and 7 being assigned dose level 1. With no DLTs, at week 7 the dose is escalated and patients 8, 9, 10 and 11 are assigned to dose level 2. With no DLTs, by week 12 the dose is escalated again and patient 12 is assigned to dose level 3. Patient 12 has a DLT and the dose is de-escalated with patient 13 to 18 being assigned to dose level 2, with two DLTs being observed among them. The estimated MTD is dose level 2 with an estimated probability of DLT of 0.27 and 90% probability interval of (0.12, 0.44). Two of the 10 patients assigned to dose level 2 have DLTs. With an accrual rate of 4 patients per month, this study takes a total of less than 6 months to complete.

4.1.1.1 Dose Limiting Toxicities for Phase 1

All patients who receive at least one dose of cobimetinib and hydroxychloroquine, with or without atezolizumab, will be evaluable for toxicity.

In order for a patient to be evaluable for DLT assessments, the patient must either incur a DLT during the DLT evaluation period, or have received at least 80% of the planned doses of hydroxychloroquine, cobimetinib, and if applicable, atezolizumab. Patients who do not fulfill one of these criteria should be considered non-evaluable for DLT assessment purposes, and be replaced.

A DLT is defined as an AE that is possibly, probably, or definitely related to study drug administration, and that is:

- Not due to the underlying malignancy;
- Has no clear evidence of an alternative etiology; and
- Meets one of the following CTCAE v.5.0 criteria during the first 28 days of hydroxychloroquine, cobimetinib, and if applicable, atezolizumab administration:
 - Any Grade ≥ 4 hematologic toxicity, except grade 4 lymphopenia, lasting ≥ 7 consecutive days
 - Grade 3 neutropenia with fever
 - Grade 3 thrombocytopenia with clinically significant bleeding
 - Any circumstance that results in dose reduction

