 - Any Grade ≥ 3 non-hematologic toxicity except:
 - Nausea, vomiting, and/or diarrhea of Grade 3 severity that resolves within 7 consecutive days with optimal prophylaxis and/or treatment;
 - Grade 3 fatigue that resolves to Grade ≤ 2 within 7 consecutive days;
 - Grade ≥ 3 alkaline phosphatase that is related to underlying malignancy (eg, bone metastasis).
 - Grade ≥ 3 asymptomatic or mildly symptomatic rash will not be considered a DLT if the event can be adequately managed with supportive care, the event resolves to become asymptomatic and/or Grade ≤ 2 within 7 days, or the event continues for longer than 7 days in a patient who has not received appropriate supportive therapy.
 - Grade ≥ 3 elevation of serum creatine phosphokinase (CPK) level will not be considered a DLT if the event is asymptomatic (i.e., not accompanied by signs, symptoms, or other laboratory abnormalities associated with rhabdomyolysis or myocardial injury) and is deemed by the investigator to be clinically insignificant.
 - Grade 3 arthralgia will not be considered a DLT if the event can be adequately managed with supportive care or the event resolves to Grade ≤ 2 within 7 days.
 - Grade 3 fever (in the absence of any clinically significant source of fever) will not be considered a DLT if the event resolves to Grade ≤ 2 within 7 days or the event continues for longer than 7 days in a patient who has not received appropriate supportive care.

- Grade 3 laboratory abnormality will not be considered a DLT if the event is asymptomatic and is deemed by the investigator to be clinically insignificant.
- Grade 3 autoimmune thyroiditis or other endocrine abnormality will not be considered a DLT if the event can be managed by endocrine therapy that would not necessitate initiation of systemic corticosteroids.
- Grade ≥ 3 total bilirubin that is not attributed to disease progression
- Grade ≥ 3 AST or ALT, but not isolated elevation in ALT (non-specific) in subjects without metastatic disease in the liver
- AST or ALT $\geq 10X$ ULN in subjects with liver metastasis
- QTc interval ≥ 501 ms confirmed by a repeat ECG
- Grade ≥ 3 Creatine Kinase with symptoms of myalgia
- Grade ≥ 2 retinal events lasting greater than 14 days or Grade ≥ 3 retinal events that are confirmed by ophthalmologic examination
- Grade ≥ 3 rash that persists despite optimal treatment, and that does not resolve to Grade ≤ 2 within 7 days.

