8.3.1 Cobimetinib-associated adverse events

For specific guidelines on how to respond to adverse events associated with cobimetinib, see Appendix 1.

The following adverse events are classified as identified risks associated with cobimetinib: serious retinopathy, left ventricular dysfunction, severe hemorrhage, rhabdomyolysis, and pneumonitis. The following adverse events are classified as potential risks for cobimetinib: severe hepatotoxicity (Grade ≥ 3), impaired female fertility, and teratogenicity and developmental toxicity. In addition, there is the possibility of drug-drug interactions in patients treated with cobimetinib. Clinical and safety data were reported that included monotherapy and combination

studies, of which key adverse events are summarized here, but for a complete review of the safety data please refer to the most current IB version.

Common (>10%) adverse events observed with Cobimetinib included bleeding, serious retinopathy, diarrhea, nausea, emesis, rash, pyrexia, chills, anemia, increased liver function enzymes, increased creatinine phosphokinase, and photosensitivity. Less common (1% - 10%) adverse events included decreased left ventricular ejection, risk of basal and squamous cell carcinoma, kertocanthoma, dehydration, hyponatremia, hypophosphatemia, hyperglycemia, and pneumonitis. Guidelines for treatment interruption or discontinuation in the case of adverse events are described in Appendix 1.

Cobimetinib should be permanently discontinued for:

- Grade 4 hemorrhage events attributed to cobimetinib
- Symptomatic or asymptomatic decrease of LVEF < 40% or $\geq 10\%$ absolute decrease from baseline after treatment break or recurrent symptomatic absolute decrease of LVEF < 10% (See Table 1 for details)
- Rhabdomyolysis or symptomatic CPK elevations not improving within 4 weeks of dose interruption
- Liver laboratory abnormalities not resolving to Grade ≤ 1 within 4 weeks of dose interruption or if Grade 4 liver laboratory abnormalities recur after initial improvement
- QTc increase meets values of both > 500 ms and > 60 ms change from pre-treatment values or 3rd occurrence of QTc > 500 ms during treatment and change from pre-treatment value remains ≤ 60 ms

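### The Phase 1 DLT window is 28 days, but no on-treatment eye examination is scheduled before Cycle 3 Day 1 (day 57), so retinal DLTs have no scheduled measurement inside the window

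*Combined protocol and SAP*

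**What the plan says.** Three places in the Phase 1 design give a four-week window. Section 4.1.1 states that "The primary endpoint is DLT in the first cycle of treatment". The statistical considerations in the same section say "the proposed toxicity evaluation period is 4 weeks". The DLT definition in section 4.1.1.1 requires a criterion to be met "during the first 28 days of hydroxychloroquine, cobimetinib, and if applicable, atezolizumab administration". The synopsis differs: it defines the MTD by DLTs up to the end of Cycle 2.

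Two retinal outcomes are DLTs under section 4.1.1.1: Grade 2 or higher events that last more than 14 days, and Grade 3 or higher "retinal events that are confirmed by ophthalmologic examination".

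The schedule of eye examinations is in footnote 9 to Table 10: "An Ophthalmologic examination should be performed during the screening period, and on cycle 3 day 1 (+ 7 days", then every 12 weeks, and at End of Study if none was done in the preceding six weeks. The examination row of Table 10 has no mark in Cycle 1 or Cycle 2.

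**The concern.** DLT is the primary Phase 1 endpoint, and it drives both the move from cohort escalation to the TITE-CRM and every later assignment. A criterion that calls for an eye examination needs one inside the window, or a stated route by which events will be found without one. The plan schedules none and states no such route in the DLT section.

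The subject matters in this trial. Section 4.1.1 names ocular toxicity as an overlap between hydroxychloroquine and its partner drugs. Section 8.3.1 says that common "adverse events observed with Cobimetinib included bleeding, serious retinopathy, diarrhea" and others. Cobimetinib and hydroxychloroquine are given at all three dose levels, so incomplete ascertainment would affect every level. A patient with an undetected retinal DLT would complete four weeks and count as free of DLT. The error would then run one way, towards a lower estimated DLT probability.

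**Working it through.** **Timing of the first examination**

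Inputs: 28-day cycles (section 4.1.1); DLT window days 1 to 28 (section 4.1.1.1); plus 7 days for the Cycle 3 examination (footnote 9); visit allowance of 3 days either way (Table 10 header).

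- Cycle 3 Day 1 = 2 × 28 + 1 = day 57. With the footnote's allowance, the examination falls on days 57 to 64.
- Gap after the window: 57 − 28 = 29 days, up to 64 − 28 = 36 days.
- With the visit allowance instead, the earliest day is 57 − 3 = 54, a gap of 54 − 28 = 26 days.
- Scheduled on-treatment eye examinations in days 1 to 28: none.
- Under the synopsis window, which ends on day 2 × 28 = 56, footnote 9 still places the examination outside. Only the three-day early allowance could bring it inside.

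**End-of-Study examination**

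It is required only if none was done within 42 days. With screening 14 days before Day 1, that point is study day 1 − 14 + 42 = 29. With the longest screening interval of 21 days, it is 1 − 21 + 42 = 22. Inside the window it can therefore reach only a patient who stops early. If that patient stopped for a reason other than treatment-related toxicity and had no DLT, section 4.1.1 has the patient replaced.

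**Comparison with other DLT criteria**

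| Criterion | Scheduled Cycle 1 measurement |
|---|---|
| Blood counts | Days 1, 8, 15, 22 (footnote 8) |
| AST, ALT, bilirubin | Days 1, 8, 15, 22 (footnote 8) |
| QTc | ECG on day 15 (footnote 6) |
| Retinal events | None (footnote 9) |

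**The duration part**

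An event present from day t has lasted 15 days on day t + 14. If the duration must be complete by day 28, then t + 14 ≤ 28, so onset must be by day 14. An event first seen on day 15 and rechecked 14 days later is rechecked on day 29, outside the window. The plan does not say whether onset or completed duration must fall within the 28 days.

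**Order of events in the first stage**

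Take the simulation's accrual of one patient a week, with no DLT. Patient 3 starts on trial day 15 and completes 28 days on trial day 42, so level 2 can open on trial day 43. Patient 1's first on-treatment eye examination is due on trial day 57. Patient 3's is due on trial day 14 + 57 = 71. Escalation can thus precede any on-treatment eye examination at level 1.

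**Direction of the effect (assumed rates)**

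The documents give neither the probability of a retinal DLT (r) nor the share found without a scheduled examination (s). Suppose the true total DLT probability is 0.30 and retinal and other DLTs are independent. The probability of other DLTs is o = 1 − 0.70/(1 − r), and the observed rate is 1 − (1 − o)(1 − r·s). For r = 0.05, o = 1 − 0.70/0.95 = 0.263; with s = 0.5 the observed rate is 1 − 0.737 × 0.975 = 0.282.

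| Assumed r | Observed rate, s = 0.5 | Observed rate, s = 0 |
|---|---|---|
| 0.02 | 0.293 | 0.286 |
| 0.05 | 0.282 | 0.263 |
| 0.10 | 0.261 | 0.222 |

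These figures show direction only. They are not estimates for this trial.

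**The case against.** The best answer is that retinal DLTs can be found in Cycle 1 without a scheduled examination. Section 9.2 requires adverse events to be sought at each contact by questioning and, as appropriate, by examination. Table 10 has such visits on days 1, 8, 15 and 22. Serous retinopathy of any grade is an event of special interest (section 8.3), and Table A1.9 refers ocular events to an ophthalmologist. Requiring confirmation can be read as confirming a suspected event rather than screening for one. Table 8, for events not listed in CTCAE, puts asymptomatic findings in Grade 1, so many events of DLT grade may produce symptoms. All of this stands. It rules out inferring that a retinal DLT cannot be detected in Cycle 1, or that an event first seen at Cycle 3 Day 1 can never be dated: a symptom history could date it. What remains exposed is the event that is asymptomatic or not reported.

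A reader might also see a contradiction with section 4.1.1, where ocular toxicities "will be monitored by required scheduled ophthalmological evaluations throughout the study period". That sentence concerns hydroxychloroquine toxicity at high cumulative doses. The calendar is compatible with that purpose, so the statement need not be withdrawn. It does not address the 28-day criterion or cobimetinib.

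Finally, a reader might apply the frequency of more than 10% in section 8.3.1 to the 18 patients to project missed DLTs. The documents do not support this: the figure pools monotherapy and combination studies, with no split by grade and no 28-day limit.

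**Conclusion.** The gap is real and specific. On the 28-day window given in sections 4.1.1 and 4.1.1.1, one component of the primary Phase 1 endpoint has no scheduled on-treatment measurement inside its window, and the first one comes 29 to 36 days later (at least 26 on the visit allowance). Ascertainment in Cycle 1 rests on an unscheduled referral.

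The consequence is possible rather than shown. Missed or undated events could bias the estimated DLT probability downward, but the size depends on two quantities the documents do not give. That the selected MTD would be too high is a further inference the documents do not establish: no selection probabilities under incomplete ascertainment are available, and the Principal Investigator may decline to escalate on clinical judgement. The point merits an amendment because the remedy is small and bears on the primary endpoint.

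**What to change.** Reconcile section 4.1.1.1, the synopsis and footnote 9 in one amendment:

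1. Use a single DLT window throughout.
2. For Phase 1, re-time an already planned on-treatment eye examination so that it falls inside that window. The sponsor decides the exact day and whether the Cycle 3 Day 1 examination is also kept.
3. State whether onset, or the completed duration of more than 14 days, must fall within the window. If completed duration is meant, the timing of the examination and any recheck has to allow for it.
4. State how an event first seen at a later scheduled examination counts towards DLT.

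The cost is text in three places and a changed visit for 18 evaluable patients. Re-timing adds no examination. Its downside is that, if Cycle 3 Day 1 is not kept, the next routine examination comes later than day 57. Keeping both means one more examination per patient.
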